4.2.2 Postal consent

The process of obtaining 'remote', valid consent is well recognised and established in specialities such as gastroenterology (for guidelines as endorsed by the British Society of Gastroenterology that conform to Department of Health recommendations see http://www.bsg.org.uk/clinical-guidelines/endoscopy/guidelines-for-postal-consenting-for-outpatient-endoscopic-procedures.html).

Previous work in this area has shown that more than 90% of patients give valid consent with this system, with almost all of the remainder providing valid consent after an opportunity for further discussion, usually about very specific points [17]. This process is particularly suited to situations where a large number of patients require consent for a procedure that is of very low risk of complications — this situation applies completely to this study protocol in which there are no potential risks to patient safety. To ensure that consent is valid, patients have to be fully informed about the procedure/study and the benefits and risks it may entail — this does not mandate a face-to-face interview and in this study will be accomplished by the patient information sheet with an option to contact the ARID research team if patients wish to discuss any points in more detail. This process also ensures ample time is given for assimilation and consideration of information. Consent will be confirmed during a telephone interview with all patients who express an interest in participation. This step will also provide an opportunity to ratify patient identity using standard data protection questions. The consent form is only a formal documentation that this decision making process has taken place, and the signed form will be returned to the ARID office in a pre-paid envelope that will then form a record of this process.

Consent will specifically include certain identifiable information being passed on to the Medical Research Information Service. Information that they would require would be the participants full name, date of birth, NHS number and address.

4.2.3 Group B – patients with liver disease

Recruitment, matching and consent

Many patients with cirrhosis in the UK are alcoholics and intravenous drug users. They tend to live a chaotic lifestyle with fluid residential addresses and limited access to telephone facilities. We therefore propose an alternative recruitment method to include this important patient group and facilitate participation. Patients will still be identified via the electronic AKI system but those who had their inpatient care delivered by the gastroenterology team will be screened for cirrhosis (using established definitions). Patients will not be approached until they have recovered from their acute illness.

Patients with cirrhosis and who meet the inclusion criteria will be approached on the ward prior to discharge and invited to participate by one of the research team. The control group will be matched to AKI patients on a 1:1 basis in terms of baseline eGFR (within the same CKD stage but as closely as possible) and age ± 5yrs. In addition they will be recruited from a similar inpatient setting. Due to the proposed three year follow up, patients over 85yrs will be excluded as the reduced life expectancy due to age alone in these patients may affect the outcome measures of mortality.

Potential subjects will receive a letter of invitation along with a comprehensive patient information sheet which they can read for 24 hours. After addressing any concerns or queries, interested patients will be asked to sign a consent form that they will sign and return to a member of the research team prior to discharge, retaining a copy for themselves. If patients do not wish to participate they will be asked to confirm this and will continue to receive standard of care.

Each patient will be assigned a unique study number that will be used to identify all data collected for the study. This will be allocated upon recruitment. A key of patient identity and study numbers will be kept on a password-protected Trust server in a password-protected file. Any information passed onto the Medical Research Information Service will be in encrypted form. A recruitment log will be maintained and the patients' GPs will be informed of their participation in the study by letter.

Consent will specifically include certain identifiable information being passed on to the Medical Research Information Service. Information that they would require would be the participants full name, date of birth, NHS number and address.

4.3 Withdrawal of Subjects

Patients will be withdrawn only if they withdraw their consent.

All patients will be included in the analyses except for those in the control group who subsequently sustain AKI during the study period, who will be excluded.

4.3.1 When and How to Withdraw Subjects

Patients who withdraw their consent will be removed from the study immediately. They will continue to receive routine care through their GP.

4.3.2 Data Collection and Follow-up for Withdrawn Subjects

Patients who withdraw will be asked to allow data collected prior to the date of withdrawal to be retained for analysis. They will also be asked to allow outcome data, including clinical events and the

results of any kidney function tests arranged by the GP, to be collected for future analysis. If a participant declines this their data will be deleted.

Patients who fail to attend for blood tests will be contacted by telephone to determine whether or not they are willing to continue. Patients without access to a telephone will be contacted by letter. If no response is received to two letters sent one month apart, the patient will be assumed to have been lost to follow-up.

4.4 Prior and Concomitant Therapy

Details of the hospital admission during which the patients were initially identified (either with AKI or screened as NAKI) will be collected from coding data on the hospital's PAS system. This will include primary diagnosis, secondary diagnoses and co-morbidity (specifically diabetes, hypertension, cardiovascular disease, active malignancy and for the liver subgroup aetiology and severity of liver disease). The patient's highest AKI stage, length of hospital stay, and discharge creatinine will be recorded. Acute dialysis treatments and dialysis independence will be determined for those patients who require acute RRT during the course of AKI.

5 Laboratory Assays

Renal function (urea and electrolytes) will be obtained at recruitment (this will be 3mnths after the episode of AKI/NAKI). Then at 1 year, 3 years, 5 years and 10 years after AKI/NAKI (approximately 9mnths, 33mnths, 57 mnths and 117 mnths post recruitment). These samples form part of routine clinical care for patients recovering after an episode of AKI or with CKD and would normally be performed by the General Practitioner. Participants will be asked not to eat meat for 12 hours prior to the blood tests (to avoid a potential effect on the creatinine assay) and will be able to have the samples taken at GP surgeries, community hospitals (including London Road) or RDH. Results will be available via the hospital results system.

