3.1 General Design

This is a long-term longitudinal observational case-control study. Basic blood tests to include measuring renal function, haemoglobin, albumin and proteinuria will be measured at study entry as well as 1 year, 3 years, 5 years and 10 years after AKI (approximately 9months, 33months, 57 months and 117 months after recruitment). Samples will also be collected and stored at each of these time points for subsequent biomarker measurement; these will consist of inflammatory markers (IL-6, high sensitivity CRP) and plus a panel of biomarkers of tubular injury (to include NGAL and IL-18). Included patients will have baseline demographics, co-morbidity and acute illness details extracted from the hospital PAS system. AKI stage and baseline renal function (that prior to sustaining AKI) will be extracted from the electronic AKI reporting system currently in clinical use at the Royal Derby Hospital. This novel system identifies all episodes of AKI from every inpatient location and also reports severity as per AKIN staging; the diagnostic accuracy of this system has been confirmed and reported previously [16].

Patients receiving acute dialysis during the episode of AKI will be identified from renal unit and intensive care unit databases; the renal database (Vitaldata) will be used to identify those patients who subsequently require chronic renal replacement therapy (RRT). The Medical Research Information

Service (MRIS, an arm of the NHS Information Centre) will be used to accurately track survival data of participants to **ten** years after the AKI episode.

A pilot study, specifically designed to test this methodology and recruitment process is currently underway, and demonstrates that the proposed recruitment, consent and matching processes are both practicable and feasible (recruitment rate ~20%, with approximately 15 participants recruited per week).

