3.2 Primary Study Endpoints

- 1. The risk of death in AKI group versus controls.
- 2. The risk of CKD progression in AKI group versus controls.

CKD progression will be defined as doubling of serum creatinine, eGFR<15mls/min or the initiation of renal replacement therapy (dialysis or transplantation).

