5.1 Biomarker analysis

Samples of EDTA plasma/serum and urine will be separated and stored at each of the **five** sample collection time points (recruitment, 9mnths, 33mnths, **57 mnths and 117 mnths** post recruitment). This will not require any additional blood or urine from the patient. Samples will be returned as usual practice to RDH central pathology laboratory where the specific study code on the iCM-generated

request form will result in removal of an aliquot of 1ml of plasma/serum and urine for storage. These samples will be placed immediately into 24/7 alarmed secure freezers in the pathology department; if additional storage space is required this will be provided in similar freezers in the medical school. Batched analysis of samples would take place subsequently to include measurement of IL-6, hs-CRP and a panel of biomarkers to include NGAL and IL-18 (final panel to be decided at time of analysis as this is a rapidly changing field). Samples will not be stored beyond the duration of the study.

6 Randomisation

Not applicable

7 Study Procedures

No procedures other than the **five** blood and urine samples (detailed in section 5) are planned.

8 Statistical Plan

Statistical advice has been sought from Derby Hospitals NHS Foundation Trust Statisticians, [name] and [name].

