8.2 Statistical Methods

Statistical analysis will be performed using SPSS v19.0 and Stata v11. Descriptive statistics will be used to summarise baseline variables in AKI and control groups. Univariate parametric or non-parametric analysis will be done to compare the two groups at baseline. Kaplan-Meier curves will be constructed to compare the primary endpoints, renal end-point and mortality between the two groups using the Log-Rank test. A Cox proportional hazard model will be used to test the effect of AKI on primary endpoints adjusted for age, gender, (race if possible), co-morbidity (diabetes, hypertension, malignancy, cardiovascular disease), baseline renal function, proteinuria, requirement for acute dialysis and multiple episodes of AKI. Conditional logistic regression will be performed for exploring the effect of AKI matched patients and secondary outcomes on the proportion of patients with CKD progression and on their mortality status at 12 months. Participants with cirrhosis will be included in the main analysis, but their co-morbid conditions will be accounted for in the statistical analysis.

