8.3 Subject Population(s) for Analysis

All patients will be included in the analyses described above except for those in the control group who subsequently sustain AKI during the study period, who will be excluded. Depending on the frequency of this occurrence a separate 'intention to treat' secondary analysis may be performed. Data from patients who withdraw (and give consent) or who die will be included until the date of withdrawal or death.

9 Safety and Adverse Events

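### Creatinine-defined progression is scheduled to be seen only at samples up to 5 years apart, while follow-up runs to death, so progression followed by death between samples is lost

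*Protocol*

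**What the plan says.** Protocol section 3.2 makes CKD progression a primary endpoint with three components: "CKD progression will be defined as doubling of serum creatinine, eGFR<15mls/min or the initiation of renal replacement therapy (dialysis or transplantation". The first two can be established only from a blood result.

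Section 5 sets the blood schedule. The first sample is early: "Renal function (urea and electrolytes) will be obtained at recruitment (this will be 3mnths after the episode of AKI/NAKI". Later samples follow: "Then at 1 year, 3 years, 5 years and 10 years after AKI/NAKI". Section 7 plans no procedures beyond the five "blood and urine samples (detailed in section 5) are planned".

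The other outcomes do not depend on attendance. Under section 3.1, "the renal database (Vitaldata) will be used to identify those patients who subsequently require chronic renal replacement therapy (RRT", and the national information service tracks survival to ten years.

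Section 8.2 states the analysis: "Kaplan-Meier curves will be constructed to compare the primary endpoints, renal end-point and mortality between the two groups using the Log-Rank test". A Cox model follows. Section 8.3 sets the end of follow-up: "Data from patients who withdraw (and give consent) or who die will be included until the date of withdrawal or death". Section 3.3 adds the proportion reaching the renal endpoint as a secondary endpoint.

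**The concern.** After the recruitment sample the gaps between scheduled creatinine measurements are 0.75, 2, 2 and 5 years. Take a participant who doubles creatinine in year 6, never starts RRT and dies in year 8. The event has happened, but no scheduled sample shows it. Kaplan-Meier and Cox credit that person with event-free time up to death and then censor. The proportion endpoint counts a non-progressor. If the same person survives, the event appears at year 10, four years late.

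This differs from the question of death as a competing event. There, death prevents the renal event; here, the renal event occurred and goes unseen. Years 5 to 10, where long-term progression should show, are the worst-measured interval. If mortality differs between the groups, so does the share of progressions lost, and the comparison is affected as well as the absolute risk.

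**Working it through.** **The plan's own figures.** The protocol gives no mortality rate and no estimate of missed events, so there is no stated figure to reproduce. Every rate below is an assumption, except that section 8.1 supplies the progression proportions 2.02% (control) and 4.41% (AKI).

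**Step 1: loss within one gap.** Let progression fall uniformly in a gap of L years, with death at hazard m per year afterwards and no RRT. The share dying before the next sample is 1 − (1 − e^(−mL))/(mL).

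| m per year | L = 0.75 | L = 2 | L = 5 |
|---|---|---|---|
| 3% | 1% | 3% | 7% |
| 5% | 2% | 5% | 12% |
| 10% | 4% | 9% | 21% |
| 15% | 5% | 14% | 30% |
| 20% | 7% | 18% | 37% |

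Example: m = 0.20 and L = 5 gives mL = 1, so 1 − (1 − 0.368)/1 = 0.368.

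**Step 2: loss over ten years, by group.** Progression has constant hazard λ from 3 months, and death has hazard m0 before progression and m1 after. With v(t) the next sample after time t, the missed share is the integral of λe^(−(λ+m0)(t−0.25)) × (1 − e^(−m1(v(t)−t))) divided by the integral of the first factor. I take λ as 4.41%/3 = 1.47% per year for AKI and 2.02%/3 = 0.67% for controls. Spreading these proportions over three years is an assumption.

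| AKI m0, m1 | Control m0, m1 | Missed: AKI, control | Ratio of progressors: true, seen |
|---|---|---|---|
| 10%, 10% | 10%, 10% | 14%, 14% | 2.11, 2.12 |
| 8%, 12% | 5%, 8% | 17%, 12% | 1.86, 1.76 |
| 10%, 10% | 5%, 5% | 14%, 8% | 1.71, 1.60 |
| 10%, 20% | 5%, 10% | 25%, 15% | 1.71, 1.50 |
| 15%, 30% | 5%, 10% | 33%, 15% | 1.41, 1.12 |

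The true ratio changes between rows because higher mortality leaves fewer AKI participants alive to progress. The effect of missed events is the difference within a row. With equal mortality there is none. The last row assumes mortality three times as high after AKI and is an extreme.

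**Step 3: what this does to a ratio of 2.0.** The seen ratio is the true ratio times the share retained in AKI over the share retained in controls. An illness-death simulation on the same visits gave these missed shares:

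- 11.8% (progression 0.5%, death 4%, death after progression 8% per year)
- 14.2% (1%, 6%, 10%)
- 19.9% (1%, 6%, 15%)

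Assigning 11.8% to controls and 14.2% to AKI gives 2.0 × 0.858/0.882 = 1.95. Assigning about 12% and 20% gives 2.0 × 0.80/0.88 = 1.82. The second pairing assumes mortality after progression nearly twice as high in AKI (15% against 8%).

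**Step 4: dating.** A progression just after the year-5 sample in a survivor is dated at year 10, so the error can reach 5 years.

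**The case against.** **RRT is captured.** A reader might infer that everyone who progresses and dies between samples is lost. The documents do not support that: anyone who starts chronic RRT first is found through the renal database. The loss concerns doubling and eGFR below 15 without RRT, so the percentages above are upper figures for the composite. This stands in full.

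**Censoring is not scoring as a non-progressor.** In Kaplan-Meier and Cox such a participant is censored at death. The label non-progressor fits only the proportion endpoint. This also stands, but the event-free time and the lost event remain.

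**The direction of bias is not given.** A reader might infer that the AKI effect is certainly pulled toward no difference. The background says only that survival after AKI may be worse, and gives no rate. Matching on eGFR and age within a similar inpatient setting does not remove such a difference, but with equal mortality the ratio does not move. Late dating alone does not favour a group, since both share one schedule.

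**Between-visit results are not forbidden.** Section 3.2 does not tie the components to study visits, section 5 calls the samples routine care and adds "Results will be available via the hospital results system", and excluding controls with later AKI implies some watch on creatinine. So the text does not settle a visit-only endpoint. Nor does it say such results count for continuing participants: section 4.3.2 names GP kidney function tests as outcome data only for those who withdraw.

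**An SAP may deal with this.** Interval-censoring detail is commonly left to an SAP, which is not shown. But sampling times, the method and follow-up to death are stated in the protocol, and the remedy improves on that stated method.

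**Conclusion.** The concern holds in limited form. Creatinine-defined progression without RRT, followed by death before the next scheduled sample, is lost from the primary renal analysis, and survivors' events can be dated up to 5 years late. For assumed mortality after progression of 3–20% per year, about 3–18% of such progressions are missed in a 2-year gap and 7–37% between years 5 and 10.

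Under-counting does not depend on a group difference in mortality. Bias in the comparison does: with higher mortality after AKI, a ratio of 2.0 might be seen as about 1.8 to 1.95. More extreme assumptions shrink it further, and equal mortality leaves it essentially unchanged. The protocol gives no mortality rates, so these are ranges and not estimates for this cohort.

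**What to change.** In sections 8.2 and 8.3:

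1. Analyse doubling and eGFR below 15 as interval-censored between the last negative and first positive value, with death after the last value modelled in an illness-death model. State this in advance, at least as a sensitivity analysis beside Kaplan-Meier and Cox.
2. As a simpler alternative to item 1, not combined with it, end renal follow-up for these two components at the last renal measurement instead of the date of death.
3. As a further sensitivity analysis, add routine creatinine results already on the hospital results system, under one extraction rule for both groups and subject to consent.

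The cost is extra analysis and data extraction, and model assumptions resting on few events. Item 3 may bring detection bias if AKI patients are tested more often, and routine samples lack the 12-hour meat restriction in section 5. The visit-only analysis should therefore be kept.

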5.1 Biomarker analysis

Samples of EDTA plasma/serum and urine will be separated and stored at each of the **five** sample collection time points (recruitment, 9mnths, 33mnths, **57 mnths and 117 mnths** post recruitment). This will not require any additional blood or urine from the patient. Samples will be returned as usual practice to RDH central pathology laboratory where the specific study code on the iCM-generated

request form will result in removal of an aliquot of 1ml of plasma/serum and urine for storage. These samples will be placed immediately into 24/7 alarmed secure freezers in the pathology department; if additional storage space is required this will be provided in similar freezers in the medical school. Batched analysis of samples would take place subsequently to include measurement of IL-6, hs-CRP and a panel of biomarkers to include NGAL and IL-18 (final panel to be decided at time of analysis as this is a rapidly changing field). Samples will not be stored beyond the duration of the study.

6 Randomisation

Not applicable

7 Study Procedures

No procedures other than the **five** blood and urine samples (detailed in section 5) are planned.

8 Statistical Plan

Statistical advice has been sought from Derby Hospitals NHS Foundation Trust Statisticians, [name] and [name].

8.1 Sample Size Determination

The original sample size for the study was based on some assumptions and information published in two studies [10, 11] so in line with the statistical plan in version 1.2 of the protocol, the sample size calculation has been repeated using one year results from the pilot study. The new sample size calculation is based on percentage change in eGFR at one year, a surrogate for subsequent CKD progression (doubling of serum creatinine or progression to CKD stage 5/dialysis). A previous study reported that 21.4% of those who experienced a 20% fall in eGFR at one year progressed to initiation of RRT [18]. Results from the pilot study have shown that 13 patients experienced such a decline in eGFR at one year in the control group as compared to 29 in the AKI group. Therefore, the estimated proportion in the control group that will progress to a doubling of serum creatinine or progression to CKD stage 5 is 2.02% as compared to 4.41% of the AKI group. Assuming a 5% significance level and 80% power this means that 430 patients will be required per group. Assuming a drop-out rate of 26% then a total of 542 patients will be required in each group.

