3.3 Secondary Study Endpoints

- 1. Proportion of patients reaching renal endpoint (doubling creatinine/ESRF)
- 2. Mortality rates at each time point.
- 3. Length of hospital stay.
- 4. Estimated glomerular filtration rate (eGFR), serum creatinine and urine protein:creatinine ratio at each time point.
- 5. Comparison of causes of death between AKI group and controls
- 6. Comparison of levels of biomarkers of tubular injury (a panel to include NGAL and IL-18) and markers of inflammation (IL-6, hs-CRP) in those with and without progression of CKD.

4 Methods

The methods are the same as for the pilot study; the only change is that we propose to collect an additional blood sample for storage and subsequent analysis at each time point.

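### CKD progression is judged only on a hard endpoint with about 50% power on the protocol's own rates, and no adequately powered progression outcome is prespecified beside it

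*Protocol*

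**What the plan says.** Section 3.2 has two primary endpoints, death and CKD progression. For the second: "CKD progression will be defined as doubling of serum creatinine, eGFR<15mls/min or the initiation of renal replacement therapy". The first secondary endpoint in section 3.3 uses essentially the same event: "Proportion of patients reaching renal endpoint (doubling creatinine/ESRF". The fourth lists eGFR, serum creatinine and urine protein:creatinine ratio at each time point, with no change from baseline and no threshold. Neither list names a percentage fall in eGFR.

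Section 8.1 starts from such a fall: "The new sample size calculation is based on percentage change in eGFR at one year, a surrogate for subsequent CKD progression". It cites an outside study in which "21.4% of those who experienced a 20% fall in eGFR at one year progressed to initiation of RRT", and reports from the pilot that "13 patients experienced such a decline in eGFR at one year in the control group as compared to 29 in the AKI group". It then projects that the proportion of controls expected to "progress to a doubling of serum creatinine or progression to CKD stage 5 is 2.02% as compared to 4.41% of the AKI group". The size follows: "Assuming a 5% significance level and 80% power this means that 430 patients will be required per group". Last comes the allowance for losses: "Assuming a drop-out rate of 26% then a total of 542 patients will be required in each group".

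**The concern.** The first objective in section 2 is the effect of AKI on CKD progression and mortality. The renal half is decided on an event that section 8.1 expects in roughly 2% to 4% of patients. If the planned size cannot support that comparison, a null result is likely even when the projected doubling of risk is real, and it could be reported as evidence that AKI does not lead to CKD progression.

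The measure on which the pilot showed a renal signal, the one-year 20% fall, is used to project event rates but is not itself a named progression outcome. Unless it is named, any later analysis of a 20% threshold is open to the criticism that the threshold was chosen after seeing the data. The biomarker comparison (secondary endpoint 6) also contrasts patients with and without progression, so it rests on the same small number of events.

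**Working it through.** **Inputs, all from section 8.1 unless noted.** Hard-endpoint proportions 2.02% (control) and 4.41% (AKI); 5% significance; 80% power; 430 per group; 26% drop-out; 542 per group enrolled; conversion factor 21.4%; pilot counts 13 and 29; 1:1 matching (section 4.2.1). Sidedness is not stated, so two-sided is assumed and one-sided also shown. The two-proportion formula treats the groups as independent.

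**1. The plan's own figure.** With p̄ = (0.0202 + 0.0441)/2 = 0.03215,

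n = [1.960·√(2p̄(1−p̄)) + 0.842·√(p₁(1−p₁) + p₂(1−p₂))]² / (p₂−p₁)²

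= [1.960 × 0.2495 + 0.842 × 0.2489]² / 0.0239² ≈ 854 per group.

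Other conventions, per group:

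| Method | Two-sided | One-sided |
|---|---|---|
| Pooled normal approximation | 854 | 673 |
| With continuity correction | 936 | 754 |
| Unpooled | 852 | 671 |
| Arcsine | 826 | 650 |
| Log-rank, Schoenfeld | 778 | 623 |
| Log-rank, Freedman | 871 | 685 |

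None gives 430. Half of 854 is 427, so a per-group number may have been read as a total; that is an inference.

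**2. Drop-out.** 430 × 1.26 = 541.8, which is the stated 542. But 542 × (1 − 0.26) = 401 remain. Retaining 430 would need 430/0.74 ≈ 582.

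**3. Power for the hard endpoint.** Power = Φ{[(p₂−p₁)√n − 1.960·√(2p̄(1−p̄))] / √(p₁(1−p₁) + p₂(1−p₂))}.

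| n per group | Expected events, both groups | Power, two-sided | Power, one-sided |
|---|---|---|---|
| 401 | 401 × 0.0643 = 25.8 | 48% | 61% |
| 430 | 27.6 | 51% | 63% |
| 542 (no losses) | 34.9 | 61% | 72% |

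The Schoenfeld log-rank formula gives 55% at 430.

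**4. The 20% fall.** The pilot denominators are not stated. Back-calculating: 13 × 0.214/0.0202 ≈ 138 controls and 29 × 0.214/0.0441 ≈ 141 AKI patients. The implied proportions are 0.0202/0.214 = 9.4% and 0.0441/0.214 = 20.6%. The same formulas give 160 per group for 80% power, and power of 99.4% at 401 and 99.6% at 430. If the AKI proportion were only 16%, power at 401 would still be about 80%.

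**5. Sensitivity of step 3 to the event rate.** If both hard-endpoint rates were 1.5 times those stated, power at 401 would be 66%; if doubled, 79%.

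**The case against.** Four points can be made on the other side.

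- A reader might infer that the study was sized on the 20% fall and then dropped it. The text does not support that. The fall is an intermediate step, and 430 is stated for the projected rates of creatinine doubling or CKD stage 5, which is close to the section 3.2 composite. Sizing target and primary endpoint match, and using a surrogate to project event rates does not oblige the study to adopt it as an endpoint. This stands.
- A reader might infer that the study will miss the decline seen in the pilot. It will not: secondary endpoint 4 covers eGFR and creatinine at each time point, and section 3.1 collects renal function from before the AKI. What remains is narrower: endpoint 4 is a list of values, not a definition of progression.
- The 2-4% rates may be too low. The 21.4% concerns start of renal replacement only, the composite also counts creatinine doubling and eGFR below 15, no horizon is given, and follow-up runs to ten years. Patients without a 20% fall at one year contribute no events to the projection. This stands as a caveat. The protocol gives no higher rate to plan on, and both rates would have to about double for power at 401 to reach 79%.
- A fall from the pre-admission baseline partly measures incomplete recovery from the index AKI, which controls did not have. The very high power is partly power to detect non-recovery. This stands, and it is why the fall should not be co-primary.

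**Conclusion.** The concern holds in limited form. On the protocol's own rates the primary renal comparison has about 51% power at 430 per group and 48% at 401, against the stated 80%; about 854 evaluable patients per group would be needed. This assumes a two-sided 5% test of two independent proportions at 2.02% and 4.41%. A one-sided reading gives 61% to 63%, still short of 80%. If ten-year event rates exceed those projected, power is higher by an amount that the protocol gives no means of fixing.

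No adequately powered progression outcome is prespecified alongside the hard composite. The 20% fall, at the back-calculated 9.4% and 20.6%, would have over 99% power at the same sizes, subject to its limits as a surrogate and to denominators that had to be inferred. The eGFR decline itself will still be measured under secondary endpoint 4.

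**What to change.** In section 3.3, add a named secondary endpoint: a fall in eGFR of at least 20% from the pre-admission baseline at 1 year, also reported at 3, 5 and 10 years. Define the baseline identically in AKI patients and controls. Label the endpoint as a surrogate that partly reflects incomplete recovery from the index AKI. Do not make it co-primary; the hard composite stays as the primary renal endpoint.

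In section 8.1, restate the actual power of the hard composite at the planned size, about 50% on the stated rates. Give the horizon to which those rates refer and the pilot denominators, and correct the 430 and the drop-out step. Say that a null result on the composite will not be read as absence of an effect on CKD progression.

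The cost is protocol wording and one further analysis of creatinine that is already scheduled for collection. The downside is a softer and noisier endpoint. It leaves the power of the primary renal comparison unchanged, which only more patients or more events would raise.
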